**Each sleep study night will consist of the following procedures:**

*Pre-sleep procedures.* Subjects will undergo a history and physical examination. They will report to the CRU at 4:00 PM and undergo anthropometric assessment including weight, height, neck, and waist circumference. At 5:30 PM, they will eat a standard dinner containing 30% fat, 50% carbohydrate, and 20% protein with kcal based upon the Mifflin-St Jeor formula. Two peripheral IVs (18 to 20 gauge) will be placed. All samples are obtained through the IV without disturbing the subject during sleep. Blood pressure will be checked at 6:30 PM, before administration of study drug. If systolic blood pressure is <90 or the heart rate is <50 then no drug will be administered. (In the event that this occurs, the study will still proceed so that CPAP and OSA nights can be compared and analyzed as a "no drug" group.) If blood pressure and heart rate are acceptable, propranolol LA 80 mg, or placebo (random order, crossover on study night 2 and 3) will be given. Participants and the investigators will be blinded to drug assignment.

*PSG setup.* On each study night from 10:30 PM until 6:30 AM, a PSG will be performed. The sleep study will include electroencephalography, electrooculography, oxygenation, respiratory effort, CPAP airflow, and transcutaneous CO2 monitoring. Respiratory effort will be measured by thoraco-abdominal movement assessed by mercury strain gauges. Surface electrodes will be placed at C3A2 and C3O1, a submental electrode, and left and right electro-oculogram will be used to stage sleep. Electrocardiograph (EKG) tracings will be recorded from three chest electrodes. Continuous measurement of oxygen saturation will be recorded using an ear oximeter (model No 472-1A, Hewlett Packard, Waltham, Mass). Transcutaneous CO2 will be monitored using a Radiometer TCM-4 device. Signals from the electroencephalograph, EKG, electromyogram, electrooculogram, respiratory strain gauge, ear oximeter and thermistors will be recorded on a computer with RemLogic software.

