and CPAP airflow. Therefore, we use a validated technique to quantify differences in FAO between studies by providing an oral liquid dose of 15 mg/kg body mass of [H31]palmitate taken with dinner. The isotope is dissolved in a warm (60 °C) liquid shake (such as Ensure®). The isotope is non-radioactive and synthetic (Cambridge Isotope Laboratories DLM-215-MPT). FAO will be quantified thereafter by hourly assessment of deuterium incorporation into plasma H2O using anisotope ratio MS (IR/MS). Subjects will also ingest 0.4 g/kg body mass of H2O (10% enriched; CIL OLM-240-10-0, Andover MA) to calculate total body water (TBW) by isotope dilution. The FAO rate will be determined by excess plasma H times TBW, while percent recovery of deuterium will be determined by dividing by dose of H administered. All tracers in this protocol are tested for microbiological contamination, and are exempt from FDA IND status (see email correspondence with FDA # PIND 132066). The isotopes of H O and [H31]palmitate are stored in the PI's laboratory. Their required amount is prepared for each participant and brought to the CRU. The [H31]palmitate is dissolved in an Ensure shake and heated in the kitchen by nursing staff or dietitian in CRU.

*Blood sampling and morning urine sample collection.* The first blood sample is taken at 5:30 PM, just before dinner and serves as a pre-medication, pre-isotope baseline. Subsequent samples are drawn hourly while the subject is awake. At 10:30 PM, when the sleep study starts, blood is sampled more frequently, at 30 minute intervals in order to capture dynamic changes in metabolism during sleep. Additional samples will be drawn towards the end of each palmitate infusion period, to ensure a plateau of isotope enrichment. Each blood sample will be 4 cc in volume and placed into lavender top tubes (EDTA) for centrifugation to obtain plasma. Cells are removed from plasma by centrifugation for 10 minutes at 1500 x using a refrigerated centrifuge. Following centrifugation, plasma will be transferred to cryovials for storage. In patients that have signed the optional consent for isolation of genetic material, we will collect an additional 16 cc (4 tubes) at 6:30 AM upon awakening since this volume is required for isolation of peripheral mononuclear cells. The final sample is obtained at 9:00 AM. .

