### Data Analysis and Anticipated Outcomes:

The primary outcomes are nocturnal glucose and FFA levels. The main independent variable is experimental condition: [CPAP], [OSA+placebo], or [OSA+propranolol]. Since glucose and FFA are measured multiple times per subject per night, we will perform mixed linear model analysis using condition as a fixed factor and subject ID as a random factor. We will also examine whether there are independent or interacting effects of time, or time x condition on trajectories of FFA and glucose. We hypothesize that OSA increases glucose and FFA levels during [OSA + placebo] nights, compared to [CPAP], or [OSA + placebo] nights. We further hypothesize that propranolol will suppress nocturnal FFA and glucose to levels similar to that of CPAP. Sleep physiology that is measured on a continuous basis will be condensed into 30 minute bins to create a parallel data structure with metabolic parameters. We will then examine whether sleep physiology (e.g. AHI, arousals, heart rate) is dynamically associated with glucose or FFA, and whether urine catecholamine levels are associated with increases in FFA or glucose. For variables measured once (RHI, morning lipid profile) or averaged together (e.g. nocturnal glucose level) we will perform one-way ANOVA for comparisons. We will also compare sleep physiology between the 3 nights, examining variables such as apnea hypopnea index, metrics of hypoxia, and sleep architecture/duration. A questionnaire will be administered each morning to assess subjective sleep quality from the night prior, and to screen for any symptoms related to study medication. These responses will be used to determine how symptomatic a subject's OSA is, whether subjective sleep quality correlates with extent of metabolic change, and whether any side effects of beta blockade were perceived.

Regarding tracer data, we predict that  $R_a$  FFA and  $R_a$  glycerol will exhibit a ~3:1 ratio reflecting typical patterns of lipolysis without significant intra-cellular recycling. Based on studies of normal sleep [39, 40], we predict that on CPAP, sleep reduces lipolysis and FAO compared to wakefulness. During CPAP withdrawal, sleep will increase lipolysis (or at least mitigate sleep-induced suppression) compared to wakefulness. We hypothesize that FAO will be reduced or unchanged by OSA. This pattern of increased lipolysis without increased FAO may lead to

ectopic lipid deposition and extracellular TG cycling (see figure).

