**7. Study Statistics**

- a. Primary outcome variable: Nocturnal FFA and glucose profile
- b. Secondary outcome variables: Morning EndoPAT, lipid panel. Sleep study parameters (e.g. total sleep time, latency, wake after sleep onset, sleep stages, AHI, oximetry, heart rate). Lipid flux data (rate of lipolysis and FFA turnover using stable isotope data; rate of fatty acid oxidation), DNA methylation profile.
- c. Statistical plan including sample size justification and interim data analysis.

**Comparisons between CPAP, [NDS + propranolol], and [NDS + Placebo]:** Primary outcome is comparison of metabolism and blood pressure for [NDS + propranolol] versus [NDS + placebo]. For metabolic parameters that are repeatedly measured during sleep (e.g. FFA, glucose) we will use mixed linear model analysis with experimental group as a fixed factor and subject ID as a random factor. Sleep physiology that is measured on a continuous basis (e.g. heart rate, AHI, SpO2) will be condensed into 30 minute bins to create a parallel data structure with metabolic parameters. We will then examine whether these sleep physiological metrics are dynamically associated with glucose/FFA level. For those parameters that are measured once per visit (e.g. RHI, lipid panel), we will compare using paired T-tests for within-subject comparisons between nights. A secondary outcome is whether CPAP and [NDS + propranolol] are similar, and this will be performed using a similar pairwise comparison. In addition, one way ANOVA will be used to ascertain whether there is a detectable difference across all three groups. Multiple regression will be used to examine associations between FFA, glucose, CPAP status, and drug adjusting for potential confounders such as diabetes, BMI, body fat (DEXA) and age. As an exploratory analysis, Pearson correlation matrices will be used to probe the interrelatedness of glucose, FFA, insulin, lipids, and sleep outcomes, followed by targeted multivariable regression. We plan an analysis of each subject's pulse rate and blood pressure after their PSG to determine whether beta blocker dosage or timing requires adjustment, which will expedite the ability to tailor the therapy if necessary.

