Sample size: In a preliminary study (n=6), Median individual heart rate during sleep \pm (SD) was 62.2 (9.2) with [OSA+placebo] and this decreased by 6.7 BPM with [OSA+propranolol]. To detect a 10% difference (reduction of 6.2 beats/min) at a power of 80% at a significance threshold of 0.05, using a one-tailed comparison, yields a sample size of 16 participants. Since we have already enrolled 5 subjects, we require 11 additional subjects. Assuming 20% dropout, we will enroll 14 additional subjects, a total of 19 participants.

Primary outcome: Median of continuously measured heart rate during sleep.

Secondary outcomes:

- augmentation index (normalized to 75 beats/min),
- heart rate variability metrics (HR standard deviation, min/max, 5th or 95th percentile)
- OSA severity (AHI, oximetry, event duration)
- sleep architecture (percent of each sleep stage during the night)
- Blood pressure
- metabolism (FFA, glucose, insulin).

Blinding:

As this is a double-blind study, above metrics will be calculated for each visit with only knowledge of visit number and not drug/placebo assignment. After these parameters have been derived, the research pharmacy will un-blind the biostatistician ([name]) and PI ([name]) to drug arm assignment to apply appropriate statistical tests, as described below.

Analysis:

For the primary analysis, we will derive summary metrics per night, per participant (i.e. median HR per night). Median heart rate per night will be compared between drug and placebo nights in a paired framework using paired student's T tests. Similar methods will be used to compare secondary outcomes. Some metrics will require additional derivation. For example, heart rate variation will be expressed as coefficients of variation, min/max and lower (5th) and upper (95th) percentiles, and visualized with Poincare plots as performed by collaborators at Johns Hopkins ².

Exploratory Analyses:

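### Pre-dose readings are taken every night but used in no outcome analysis: a possible precision gain for propranolol versus placebo is left unspecified

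*Protocol*

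**What the plan says.** **Pre-dose measurements.** Protocol section 4, under blood sampling, has a first sample at 5:30 PM, ahead of dinner, that "serves as a pre-medication, pre-isotope baseline". Under pre-sleep procedures: "Blood pressure will be checked at 6:30 PM, before administration of study drug". The hold rule there, "If systolic blood pressure is <90 or the heart rate is <50 then no drug will be administered", implies that heart rate is read at the same check. That rule is the only use stated for the 6:30 PM readings.

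**Protocol analyses.** Section 7c specifies "mixed linear model analysis with experimental group as a fixed factor and subject ID as a random factor" for repeatedly measured FFA and glucose. The data analysis part of section 4 adds: "We will also examine whether there are independent or interacting effects of time, or time x condition on trajectories of FFA and glucose". Once-per-visit measures get paired t-tests, plus one-way ANOVA across the three conditions. A multiple regression is described as "adjusting for potential confounders such as diabetes, BMI, body fat (DEXA) and age". No pre-dose value is listed.

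**SAP analyses.** Primary: "Median heart rate per night will be compared between drug and placebo nights in a paired framework using paired student's T tests". Secondary outcomes, which include blood pressure, FFA and glucose, are handled similarly. The exploratory mixed models contain drug, time and drug-by-time, with random intercepts and slopes.

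**Near misses.** Section 6a of the protocol refers to a basal heart rate in the dose-adjustment criterion, but takes it from the placebo night. The pre-infusion sample used for isotope background enrichment serves the tracer calculations, not the four outcomes considered here.

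**The concern.** Pairing removes stable differences between people. It does not remove variation within a person from one night to the next, and that variation is the error term in a paired comparison. Visits may be 4 days to 3 weeks apart, and each OSA night follows two home nights without CPAP, so a participant's state on arrival can differ between the propranolol and placebo nights. A pre-dose reading taken the same evening is the natural covariate for that component, and the protocol itself labels one such sample a baseline.

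The SAP's primary comparison needs 16 people. If the pre-dose value is informative, leaving it out wastes precision that needs no new procedure. If it is added only after results are seen, the choice could look data-driven. That risk is concrete here: section 4c of the protocol unblinds the investigator after six completers, and the SAP already reports heart rate by condition for a preliminary group of six.

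**Working it through.** **Inputs.** From the SAP sample-size paragraph: effect 6.2 bpm, SD 9.2 bpm, one-sided alpha 0.05, power 80%, N = 16. The SD is printed beside the placebo-night mean of 62.2, so treating it as the SD of paired differences is an assumption (step 4). Also assumed is r, the correlation across participants between the drug-minus-placebo difference in the pre-dose value and the drug-minus-placebo difference in the outcome. The documents do not give r.

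**1. Reproduce the plan's figure.** d = 6.2 / 9.2 = 0.674. For a paired t-test with n = 16, the noncentrality is 0.674 × √16 = 2.696 on 15 df, with one-sided critical value 1.753. Power is 82.3%, and 16 is the smallest n that reaches 80%. The SAP's N therefore corresponds to an unadjusted test with 9.2 as the SD of differences.

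**2. Add the covariate.** Regress the outcome difference on the pre-dose difference; the intercept is the adjusted drug effect. Relative to the unadjusted analysis, the standard error is multiplied by

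f = √(1 − r²) × √(1 + 1/(n − 3)) = √(1 − r²) × 1.038,

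where the second term is the average cost of estimating the slope. Noncentrality becomes 2.696 / f on 14 df (critical value 1.761).

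| r | f | noncentrality | power, one-sided | N for 80% |
|---|---|---|---|---|
| unadjusted | 1 | 2.696 | 82.3% | 16 |
| 0 | 1.038 | 2.598 | 79.5% | 17 |
| 0.3 | 0.990 | 2.723 | 82.7% | 15 |
| 0.5 | 0.899 | 2.999 | 88.6% | 13 |
| 0.7 | 0.741 | 3.637 | 96.5% | 10 |

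Simulation of the same comparison agrees to within about 0.3 points. The analysis breaks even near r = 0.3. At r = 0 it loses 82.3 − 79.5 = 2.8 points; at r = 0.5 it gains 6.3; at r = 0.7 it gains 14.2. Two-sided at r = 0.5, power goes from 71% to 80%.

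**3. Why a covariate and not a change score.** With equal SDs, subtracting the baseline multiplies the SD by √(2 − 2r). One-sided power at n = 16 is then 56.9% at r = 0, 70.2% at 0.3, 82.3% at 0.5 and 95.3% at 0.7. The change score loses power unless r exceeds 0.5, and at every value shown it is below the covariate analysis.

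**4. Sensitivity to the SD.** If 9.2 is the spread between people on one night and the two nights correlate at ρ with equal SDs, the SD of differences is 9.2 × √(2 − 2ρ), which equals 9.2 only at ρ = 0.5. One-sided power at n = 16, unadjusted and then adjusted at r = 0.5:

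- ρ = 0.3: SD 10.9, 70.2% to 77.8%
- ρ = 0.5: SD 9.2, 82.3% to 88.6%
- ρ = 0.7: SD 7.1, 95.3% to 97.9%
- ρ = 0.8: SD 5.8, 99.2% to 99.8%

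The gain in power is thus conditional on two correlations that the documents do not report.

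**5. Which contrast.** On both drug nights the pre-dose reading follows the same CPAP withdrawal and precedes dosing, whether dosing comes just after the 6:30 PM check (section 4) or at 7:00 PM (section 6a). For CPAP versus OSA, the OSA-night reading comes after two home nights off CPAP. It is already downstream of the condition being compared, and adjusting for it could remove part of the OSA effect.

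**The case against.** The strongest reply is that nothing here is an error. Order is randomised and every comparison is within person, so the paired t-test is valid as written. That stands. A reader might infer from an unused baseline that the treatment estimates are biased or the analysis invalid; the documents do not support that.

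Second, the benefit is unproven. The heart-rate reading is a single awake value at 6:30 PM, about an hour after dinner, set against a median over sleep. The blood sample is taken before a standard meal, with the sleep samples hours later. A low r is plausible, and adjustment would then gain nothing or cost a little. That also stands, and it is why the range is shown with its loss.

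Third, some facts are inferred. The protocol does not say that the 5:30 PM sample is assayed for FFA and glucose, although calling it a baseline in that series suggests so. A recorded 6:30 PM heart rate follows only from the hold rule. Nor would it be right to read the planned mixed models as holding only condition and subject: both documents add time and its interaction, and the SAP adds random slopes. None of those terms carries the pre-dose value, so the central observation survives.

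**Conclusion.** The point holds as a missed option for precision, not as a flaw in validity. No outcome analysis of FFA, glucose, heart rate or blood pressure uses the same-night pre-dose value.

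The size is quantified for heart rate only: between about 3 points of power lost and 14 gained as r runs from 0 to 0.7, from 82% unadjusted. It assumes n = 16, a one-sided test, a 6.2 bpm effect and an SD of differences of 9.2. No figure is offered for FFA, glucose or blood pressure. It would be tempting to read 89% as the power the trial could have had; that needs r = 0.5, for which the documents give no support. The case for acting is that the downside is small, the possible gain is larger, and the readings appear to be in hand already.

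**What to change.** Before the remaining assignments are unblinded, add to the SAP, for propranolol versus placebo only:

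- **Paired analyses:** regress the outcome difference on the pre-dose difference and report the intercept. Do not centre the pre-dose difference, because that returns the unadjusted mean.
- **Mixed models:** add the pre-dose value, split into the subject's mean over the two drug nights and that night's deviation from it.
- **Covariates:** the 5:30 PM value for FFA and glucose, and the 6:30 PM value for heart rate and blood pressure, after confirming that these are assayed and recorded.
- Use a covariate, not a change score, and report the unadjusted paired result alongside.
- State that the CPAP contrast is not adjusted, and why.

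If the team prefers to leave the baseline unused, one sentence giving the reason would settle the matter. The cost is SAP wording, one degree of freedom in the paired regression, and about 3 power points if the baseline turns out to be uninformative. No new procedure is needed if the readings are already assayed and recorded.

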#### **Morning procedures:**

*EndoPAT.* The stable isotope infusion is stopped, the 09:00 AM blood draw is obtained, the IV is discontinued. The subject will report to the EndoPAT in the CRU at about 09:15 AM, and will rest awake in the supine position. A blood pressure cuff is placed on the non-dominant arm while the contralateral arm is used for control comparisons. Baseline measurements will be taken for 5 minutes, during 5-min occlusion of the brachial artery by inflation of the automated cuff 50 mmHg above systolic blood pressure, and for 5 minutes upon release of the cuff. Endothelium-mediated vasodilation is assessed using a finger pulse wave amplifier. The RHI and the augmentation index will be derived by software and used as metrics of endothelial function and arterial stiffness respectively. After the test is finished, breakfast will be served and the patient is discharged from the CRU.

*This portion of the study is completed: [OGTT.* The subject will report to the nurse's station after EndoPAT is completed. From the indwelling IV, blood samples will be obtained. The patient will be given a 75 g glucose solution to drink within 5 minutes. Blood samples of insulin and glucose are then collected in EDTA tubes at 30, 60, 90, and 120 minutes after drinking the glucose solution, and centrifuged to obtain plasma. They will be asked, if possible, to remain awake during the OGTT. After OGTT, breakfast is served and the participant is discharged from the CRU.]

*Dual-energy X-ray absorptiometry (DEXA).* Each subject will undergo a DEXA scan to estimate fat mass, which will be one of the variables analyzed as a predictor of FFA elevation. Each participant only needs 1 DEXA scan for the study and this can be performed on any one of the visits. If necessary for staffing reasons, the DEXA can be performed at a different time such as the afternoon or evening before sleep.

**Post-test procedures:** To minimize the impact of sleep loss on driving safety, subjects are asked to either (1) arrange for an alternate means of transportation home (this is mentioned on the consent or to (2) sleep as needed for up to 4 additional hours before discharge. Repeat sleep tests may be requested from the subject under the following circumstances: (1) A technical problem with data acquisition including PSG lead failure/artifacts, incomplete blood collection from IV insertion or maintenance problems. (2) Poor sleep efficiency <50% of time in bed. (3) inadequate resumption of OSA (AHI>15) or its effective treatment with CPAP (AHI<10). If sleep studies meet these criteria and a repeat test is deemed necessary by the PI, then the repeat testing will be scheduled at least 1 week following the inadequate study.

[figure not shown]

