Blood samples will be collected at the intervals depicted (every 30-60 min, with additional samples towards end of each palmitate infusion period to verify isotopic steady-state) and analyzed for isotope enrichment by gas chromatography-mass spectrometry (GC/MS). Infusion of [ $^{13}\text{C}_3$ ]glycerol and quantification its enrichment in plasma of will be used to calculate lipolysis ( $R_a$  glycerol) throughout the night. Infusion of [ $^{13}\text{C}_{16}$ ]palmitate ( $0.04 \mu\text{mol}\cdot\text{kg}^{-1}\cdot\text{min}^{-1}$ ; Sigma-Aldrich, St. Louis, MO ) will be infused for 1-hour intervals at 9-10 PM (pre-sleep), 12-1 AM (early night), 5-6 AM (late night), and 8-9 AM (awake). Palmitate isotope will be bound to human albumin prior to infusion to facilitate steady-state infusion rates. Plasma enrichment of [ $^{13}\text{C}_{16}$ ]palmitate will be measured by GC/MS and used to calculate FFA turnover.  $R_a$  glycerol and  $R_a$  palmitate will be calculated from non-steady state Steele equations.  $R_a$  FFA will be derived from  $R_a$  palmitate based on the fractional contribution of palmitate to the total FFA concentration, as determined by GC.  $R_a$  FFA will be determined for each of the four infusion periods based on the average plasma [ $^{13}\text{C}_{16}$ ]palmitate enrichment during the last 3 samples of each infusion period.

**Ingestion of [ $^2\text{H}_{31}$ ]palmitate:** Conventional FAO assessment requires breath collection (e.g. enrichment of  $^{13}\text{CO}_2$  from infused [ $^{13}\text{C}$ ]palmitate), and calorimetry which would disrupt sleep, respiratory monitoring,

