In total, the blood collected will be approximately 30 samples x 4 mL = 120 mL. For patients that consent to isolation of genetic material, the total will be 136 cc. This quantity is less than half the volume of blood given during a donation (350 mL). A morning urine sample will be collected for measurement of catecholamines. The final blood sample will be drawn at 9 AM, after which the IV will be removed, and the subject will be discharged from the CRU. Samples will be frozen at -80°C for research pertaining to metabolic effects of OSA, with the consent of participants.

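### The protocol stops the isotope infusion before the 9:00 AM draw, so awake-morning Ra FFA may be overestimated if that sample enters the three-sample average

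*Protocol*

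**What the plan says.** Protocol Section 4 (stable isotope ingestion and infusions) schedules four one-hour palmitate infusions: 9-10 PM, 12-1 AM, 5-6 AM and 8-9 AM, the last labelled awake. Glycerol tracer runs continuously through the night. Ra for both tracers "will be calculated from non-steady state Steele equations", and Ra FFA for each window rests on the average palmitate "enrichment during the last 3 samples of each infusion period".

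On sampling, the same section says "Subsequent samples are drawn hourly while the subject is awake". Draws are half-hourly from 10:30 PM, and an unspecified number of extra draws fall near the end of each palmitate infusion. It closes with "The final sample is obtained at 9:00 AM" and a budget: "In total, the blood collected will be approximately 30 samples x 4 mL = 120 mL".

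The Morning procedures text (EndoPAT) then gives the end-of-visit order: "The stable isotope infusion is stopped, the 09:00 AM blood draw is obtained, the IV is discontinued". No interval between stop and draw is given.

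Under Data Analysis and Anticipated Outcomes, the protocol predicts that on CPAP "sleep reduces lipolysis and FAO compared to wakefulness". Off CPAP it predicts that sleep raises lipolysis, or at least weakens its suppression.

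**The concern.** An isotope-dilution estimate of Ra needs the tracer to be running when the sample is taken, or the calculation to allow for its having stopped. The written order takes the last sample of the 8-9 AM window after the tracer is off. If that sample is averaged with two earlier ones at the full infusion rate, mean enrichment is too low and Ra too high.

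The 8-9 AM window is one of two awake references for the sleep-versus-wake predictions. The other, 9-10 PM, follows a 5:30 PM dinner, so 8-9 AM is the only awake window after the overnight fast. An upward error confined to it would exaggerate suppression by sleep on CPAP and hide a rise during sleep off CPAP.

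**Working it through.** **Step 1. Is the 9:00 AM sample one of the three?** The text does not say, so count the written schedule, assuming that the hourly draws continue on the half-hour from the 5:30 PM baseline.

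- 5:30 to 9:30 PM, hourly: 5
- 10:30 PM to 6:30 AM, half-hourly: 17
- 7:30, 8:30 and 9:00 AM: 3
- Scheduled total: 5 + 17 + 3 = 25

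Scheduled samples inside each palmitate window, counting the end point, and extras needed to reach three:

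| Window | Scheduled | Extras |
|---|---|---|
| 9-10 PM | 1 | 2 |
| 12-1 AM | 2 | 1 |
| 5-6 AM | 2 | 1 |
| 8-9 AM | 2 | 1 |

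Extras total 5, and 25 + 5 = 30. At 4 mL each this is 120 mL, which reproduces the stated budget. On this count the 8-9 AM samples are 8:30, one extra and 9:00, so the 9:00 AM draw is needed to make three.

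**Step 2. Direction.** At plateau, Ra = F / E, where F is the infusion rate and E the enrichment. After the stop E falls, so with F unchanged Ra rises. The non-steady-state Steele form does not remove this by itself: with F unchanged, a falling E makes the derivative term add to Ra. Entering F = 0 for the post-stop sample would avoid the bias, but the protocol does not say which F is used.

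**Step 3. Size for the three-sample average.** Let d be the delay from stop to draw and h the enrichment half-life, with the other two samples at plateau. The third sample keeps a fraction 2^(-d/h), so

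relative bias = 3 / (2 + 2^(-d/h)) - 1.

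Neither d nor h is in the documents. One guide to h is to assume that a sample 30 minutes into an unprimed infusion has reached 95% of plateau. Then k ≥ ln(20)/30 = 0.0999 per minute, and h ≤ ln(2)/0.0999 = 6.9 minutes. The 95% criterion is itself an assumption, so a longer half-life is shown too.

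| Assumed h | d = 0 | 1 min | 2 min | 5 min |
|---|---|---|---|---|
| 3 min | 0% | 7.4% | 14.1% | 29.6% |
| 5 min | 0% | 4.5% | 8.8% | 20.0% |
| 6.9 min | 0% | 3.3% | 6.5% | 15.2% |
| 10 min | 0% | 2.3% | 4.5% | 10.8% |

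Worked entry, h = 5 and d = 2: 2^(-0.4) = 0.758, and 3/2.758 = 1.088. The ceiling, with all label gone from the third sample, is 3/2 - 1 = 50%.

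These figures are for palmitate. No three-sample rule is given for glycerol, so a single post-stop value would not be diluted by two good ones. I put no figure on it.

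**Step 4. Does it shift awake against sleep?** On the same schedule, 1:00 AM and 6:00 AM also fall at the moment their infusions end. The protocol does not say whether those samples, or the last 9-10 PM sample, are drawn before or after the stop. If they too follow the stop, with similar delay and turnover, the bias is about equal in those windows and the awake-versus-sleep difference largely cancels. If they precede it, the bias stays in the morning window.

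**The case against.** A reader might infer that awake Ra FFA is overestimated relative to the sleep windows. The documents do not support that as a flat statement, and several objections stand.

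- **Membership is inferred.** The protocol refers to depicted sampling intervals, and the figure is not available here. The total is only approximate. Section 8 (Phlebotomy) gives 116 cc, which is 29 samples at 4 mL. That matches 25 plus one extra per window and leaves 9-10 PM with two samples. Two extras before 9:00 AM in the last window would make 31, still about 30. The count makes membership likely and no more.
- **A strict reading could exclude the sample**, because a post-stop draw is arguably not part of the infusion period. That avoids the bias, but on the 30-sample count it leaves two samples and the three-sample rule cannot be met. The two texts then still need reconciling.
- **The delay may be negligible.** Infusion end and draw are both set for 9 AM, and the sentence may be a list of near-simultaneous steps. At zero delay there is no bias.
- **The other windows are silent**, as Step 4 shows, so an error confined to the morning is not established.
- **Reach is limited.** Lipid flux is a secondary outcome in Protocol Section 7 and is not among the outcomes listed in the SAP. The 9-10 PM window is a second awake reference that the Morning procedures order does not touch.

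What survives is the written order itself. Followed literally, with any real delay and F unchanged, it can push Ra in one direction only.

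**Conclusion.** The point holds conditionally. If the 9:00 AM sample is one of the three and F is entered unchanged, awake-morning Ra FFA may be overestimated: by 0% with no delay, and by about 3% to 9% at a 1 to 2 minute delay with an assumed half-life of 5 to 7 minutes. Longer delays or shorter half-lives give more. The final Ra glycerol value is open to the same error.

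A bias in the sleep-versus-wake comparison is possible but not shown. It would also go too far to infer that the propranolol or CPAP contrasts are compromised: the same window is compared across nights, so a common error mostly cancels if delay and turnover are similar, although a delay that varies between nights would add noise. Neither the protocol's primary outcomes (nocturnal FFA and glucose) nor the SAP's (median heart rate during sleep) use these calculations.

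**What to change.** Reorder the Morning procedures sentence so that the 9:00 AM sample is drawn while both infusions are running, then stop them and remove the IV. State the same draw-then-stop order for the end of every palmitate window. It would also help to list the three sampling times per window and the F entered for each sample.

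For completed nights, check the recorded stop and draw times. Only where the 9:00 AM sample was drawn after the stop, omit it from the Ra FFA and Ra glycerol calculations, or repeat them without it as a sensitivity analysis. Dropping it from every night unchecked could discard valid plateau samples.

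The cost for future nights is a short wording change with no extra blood. For affected past nights it is one fewer sample in that window's average.
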